### 8.5 Analysis Populations

The following analysis sets will be defined for the Phase 2b portion of the study.

#### 8.5.1 Modified Intent-to-Treat Analysis Sets

All randomized subjects who receive at least 1 dose of KPL-716 or placebo and have at least 1 daily WI-NRS score in the double-blind Treatment Period will be included in the modified

intent-to-treat (mITT) analysis set. Efficacy analyses will be based on the mITT analysis sets. All mITT analyses will be based on each subject's randomized treatment assignment.

#### **8.5.2 Safety Analysis Sets**

All randomized subjects who take at least 1 dose of KPL-716 or placebo will be included in the Safety Analysis Set. Safety analyses will be based on the treatment (KPL-716 or Placebo) that was administered to each subject.

#### **8.5.3 Per Protocol (PP) Analysis Sets**

All mITT subjects who have no important protocol deviations that may potentially bias efficacy analyses of the study will be included in the PP set.

#### **8.5.4 Pharmacokinetic Analysis Sets**

Subjects who received KPL-716 and who had at least one PK sample will be included in the PK population.

### **8.6 Analysis of Efficacy**

All efficacy analyses will be performed on the mITT analysis set. The primary efficacy endpoint in Phase 2b will be analyzed with ANCOVA including treatment as fixed effect, baseline WI-NRS, and randomization stratification factors as covariates.

For key secondary efficacy endpoints, the difference of proportions and the corresponding 95% CI for the difference of proportions will be displayed. Treatment groups will be compared using a Cochran-Mantel-Haenszel test controlling for the randomization stratification variables.

The analyses of primary and key secondary efficacy endpoints will be repeated using the PP set to assess the sensitivity of the results to important protocol deviations that could potentially bias the analysis. All efficacy data will be listed by subject.

Details will be specified in the Phase 2b SAP.

### **8.7 Analysis of Safety**

All safety analyses will be conducted based on the Safety Analysis Set. Summary tables will be done for safety endpoints (treatment emergent AEs, labs, vital signs, etc.). All safety data will be listed by subject. Details for the analysis of safety data will be provided in the SAP.

#### **8.7.1 Adverse Events**

Adverse events will be mapped to preferred term (PT) and system organ class (SOC) using the most up to date Medical Dictionary for Regulatory Activities (MedDRA). AEs that begin after the first administration of study drug or existing AEs that worsen after the first dose of study medication are considered TEAEs. The number and percentage of subjects reporting TEAEs will be summarized for each treatment group by MedDRA SOC and PT, by severity, and by relationship to study treatment. The number and percentage of subjects with serious AEs, and the number and percentage of subjects with AEs leading to treatment

discontinuation will also be summarized for each treatment group by MedDRA system organ class and preferred term.

#### **8.7.2 Clinical and Laboratory Events and Analyses**

Continuous laboratory data will be examined for trends using descriptive statistics of actual values and changes from baseline over time in each treatment group. These data will also be categorized as low, normal, or high based on the reference ranges of the central laboratory. Shift tables from baseline to each post baseline time point will be presented.

#### **8.7.3 Vital Signs**

Vital signs will be summarized using descriptive statistics of actual values and changes from baseline over time. The incidence of clinically notable vital signs will be summarized by treatment group.

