4.7. Safety Analyses

Safety analyses will consist of data summaries for clinical and laboratory parameters, vital sign, and for adverse events (AEs). Adverse events will be coded using MedDRA of the version at database lock. Laboratory parameters, vital signs, and ECG data will be summarized as descriptive statistics by treatment, visit, and study period. Safety summaries will be based on the safety analysis set.

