4.7.2. Clinical Laboratory Tests

Blood and urine samples will be collected for clinical laboratory evaluations (including clinical chemistry, hematology, urinalysis, and serology) at the time points specified in Protocol

Appendix 1. The data collected in different units were converted to SI units (the International System of Units) for summary.

The following summaries by study periods will be provided by laboratory category of chemistry, hematology, and urinalysis.

- Numeric laboratory values will be summarized as descriptive statistics for both actual value and change from baseline (post baseline minus baseline) by week. If lab values are recorded as <xx, the limits of xx will be used for summary.
- Shift table summarizing subject incidence of laboratory normal range (Low, Normal, High) at baseline contrasted with lowest or highest post baseline. Parameters with bidirectional abnormality (low and high) will be presented by post baseline lowest and highest.

All laboratory data will be listed.

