4.7.3. Vital Signs

All vital signs including weight, pulse rate, body temperature, respiration rate, and systolic and diastolic blood pressure will be summarized. Descriptive statistics will be presented for the observed value and the change from baseline by treatment and visit if applicable. For repeated assessments at a visit, the average of these values will be taken for the summary at the visit.

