4.7.4. Electrocardiograms

Numeric 12-lead ECG parameters will be summarized. Descriptive statistics will be presented for the observed value and the change from baseline at each scheduled visit. Incidence of a normal to abnormal shift for overall ECG interpretation from baseline to worst post baseline will also be summarized by periods. Findings of other categorical parameters will be listed. For repeated assessment, if interpretations are the same, the last value will be taken for numerical assessment for summaries. If interpretations are different, the last value with the abnormal interpretation will be used for summary.

QT interval corrected for heart rate using Fridericia's method - Below incidence will be summarized:

- QTcF interval >500 msec
- QTcF change from the baseline (pre-dose) is >60 msec

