6. CHANGE FROM ANALYSIS PLANNED IN PROTOCOL

There are no changes from the statistical analyses in protocol.

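### The SAP drops the protocol's by-arm incidence of clinically notable vital signs without declaring it, and the Day 1 post-dose reading falls in no visit window

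*Protocol*

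**What the plan says.** **Planned summary.** Protocol 8.7.3 asks for descriptive statistics of vital signs and then adds: "The incidence of clinically notable vital signs will be summarized by treatment group". Protocol 8.7 leaves the detail of the safety analysis to the SAP.

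**What the SAP carries.** SAP 4.7 says: "Laboratory parameters, vital signs, and ECG data will be summarized as descriptive statistics by treatment, visit, and study period". SAP 4.7.3 says: "Descriptive statistics will be presented for the observed value and the change from baseline by treatment and visit if applicable", and "For repeated assessments at a visit, the average of these values will be taken for the summary at the visit". Neither section mentions an incidence of notable values or gives thresholds. SAP Section 6 says: "There are no changes from the statistical analyses in protocol".

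**Neighbouring domains.** SAP 4.7.2 gives laboratory data a shift table, with normal-range category "at baseline contrasted with lowest or highest post baseline". SAP 4.7.4 says of the ECG: "Incidence of a normal to abnormal shift for overall ECG interpretation from baseline to worst post baseline will also be summarized by periods". It also counts two QTcF criteria, one of them "QTcF interval >500 msec".

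**Timing of the readings.** The protocol takes vital signs before and after every dose (Synopsis, Randomization and Dosing; Section 4.1.2.2). The second reading comes at the end of the one-hour observation (Appendix 1, footnote 7). SAP 3.1 limits the safety baseline to values before the first dose. The footnote to SAP Table 6 closes the Baseline row at the date and time of that dose, and the Week 2 row starts on Day 2.

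**The concern.** Safety and tolerability against placebo is a secondary objective in both documents (Protocol 2.2, SAP 1.1.2). Means and quartiles by visit do not show how many subjects in each arm crossed a clinically relevant limit. The incidence table was planned to show that. If the SAP is followed as written, the table is not produced, and a reader who relies on Section 6 would not know it had been planned. If it is added later, after the blind is broken, its thresholds would be chosen with the results in view.

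The Day 1 gap adds to this. The reading one hour after first exposure is mandated for every dosed subject, yet the SAP gives it no place in any by-visit table.

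**Working it through.** There is no sample size, power or alpha figure to reproduce. The check is a comparison of texts followed by an assignment of readings to windows.

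**Step 1: outlier summaries, by domain**

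| Domain | Protocol | SAP |
|---|---|---|
| Laboratory | Shift tables (8.7.2) | Shift to lowest or highest post-baseline value (4.7.2) |
| ECG | No separate analysis subsection in 8.7 | Shift to worst post-baseline interpretation, plus two QTcF criteria (4.7.4) |
| Vital signs | Incidence of notable values by arm (8.7.3) | None (4.7, 4.7.3) |

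Incidence tables for vital signs: 1 planned in the protocol, 0 in the SAP. Changes declared in SAP Section 6: 0.

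**Step 2: readings against the windows for vital signs in SAP Table 6**

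Inputs: treatment day = date − first dose date + 1 (SAP 3.2). The windows are Baseline ≤ 1 and up to the first dose; Week 2 = 2–22; Week 4 = 23–43; Week 8 = 44–71; Week 12 = 72–99; Week 16 = 100 to first OLE dose. Visits are placed on their nominal days.

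- Day 1 pre-dose: Baseline.
- Day 1 post-dose: treatment day 1 − 1 + 1 = 1 if the first dose is on Day 1. It is too late for Baseline (after the dose) and too early for Week 2 (1 < 2), so it has no window.
- Day 15: Week 2 (no dose at this visit).
- Days 29, 57 and 85, pre-dose and post-dose: both readings in Week 4, Week 8 and Week 12 respectively.
- Day 113 before the first OLE dose: Week 16.
- Day 113 after the first OLE dose: depends on the reading of Table 6. It is in Week 16 if that window ends on the date of the dose, and in no window if it ends at the time of the dose, because Table 7 starts on the following day.

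**Step 3: size of the Day 1 gap**

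SAP 1.5 plans about 45 subjects in each of 4 arms.

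- All arms: 4 × 45 = 180 Day 1 post-dose readings.
- Active arms: 3 × 45 = 135. Placebo: 45.
- With four double-blind doses and nobody missing one, there are 4 × 180 = 720 post-dose readings, so Day 1 is 180/720 = 25% of them. Missed or stopped doses would raise that share. The documents do not give their timing or number, so no upper figure is offered.

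**Step 4: two readings in one window (Weeks 4, 8 and 12)**

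Let d be the change from the pre-dose to the post-dose reading on the same day; the documents give no value for it.

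- If SAP 4.7.3 averages them: (pre + pre + d)/2 − pre = d/2.
- If SAP 3.3 applies (nearest to target day, and the later one when tied): (pre + d) − pre = d.

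The two rules differ only if the averaging sentence covers a pre-dose and post-dose pair.

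**The case against.** The strongest case against giving this weight is that nothing inferential depends on it. The tables are descriptive and the rules are the same in every arm. SAP Section 3 lists all safety data by subject, and adverse events are recorded at the one-hour observation and summarized as TEAEs. That stands and it limits the severity. It does not remove the point, because listings are not a by-arm comparison and adverse event capture depends on investigator judgement.

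One could also argue that the Day 1 post-dose reading slips into Baseline by date. SAP 3.1 rules that out, since a baseline value must precede the first dose.

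Four stronger readings are tempting, and the documents do not support them.

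- **That the omitted table is the only vital signs summary independent of visit windows, and so would have caught the Day 1 reading.** Protocol 8.7.3 says only that it is by treatment group. It does not say whether incidence is counted per reading, per visit or on the worst value.
- **That pre-dose and post-dose values at Weeks 4, 8 and 12 will be blended.** Protocol 7.5.4 has measurements taken singly and repeated when out of range, which gives the averaging sentence a natural meaning limited to retests. The wording needs clarifying; it is not a shown error.
- **That the first OLE post-dose reading is lost.** Treatment day is built from dates, and in Table 6 only the Baseline footnote mentions a time, so Week 16 can hold that reading. The opposite view rests on the safety period ending at the first OLE dose (SAP 3.3). Either can be argued.
- **That separate pre-dose and post-dose tables at every visit are owed.** No objective, endpoint or analysis section asks for that comparison.

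**Conclusion.** Two points hold on the text. First, a by-arm safety summary planned in Protocol 8.7.3 is absent from the SAP, and the SAP's statement of no changes is incorrect for it. This needs no assumption. Second, the Day 1 post-dose vital signs, about 180 planned readings with 135 on active drug, have no window in Table 6 and enter no by-visit summary. This rests on the planned 45 per arm, on every randomized subject being dosed and measured, and on Table 6 reading as set out in the working.

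The averaging rule and the first OLE post-dose reading need clarification only. The consequence is limited to descriptive safety tables, with no efficacy test affected. It is a minor correction to the SAP, worth making before unblinding because the criteria must not be chosen afterwards.

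**What to change.** 1. In SAP 4.7.3, restore the incidence of clinically notable vital signs by treatment group and study period. State the criteria and fix them before unblinding. Count individual post-baseline readings, including Day 1 post-dose. If the sponsor prefers not to produce the table, declare the omission in SAP Section 6.
2. Add a Day 1 post-dose time point to Table 6.
3. Clarify in SAP 4.7.3 that averaging applies to retests within one time point. Pre-dose and post-dose readings at Weeks 4, 8 and 12 are then not blended, and the rule does not conflict with the later-value rule in SAP 3.3.
4. Clarify in SAP 3.3 whether the first OLE post-dose reading belongs to Week 16 or to the OLE period.

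The cost is SAP wording, one set of criteria, one incidence table and one added time point. All the data are already collected under the protocol.

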#### **8.7.4 Physical Examination**

Clinically significant new or worsened physical examination abnormalities following treatment will be recorded as AEs and will be reflected in the summary of AEs.

#### **8.7.5 Concomitant Medications**

Concomitant medications will be coded using WHO Drug Dictionary and will be classified by Anatomical Therapeutic Chemical (ATC) classification level 4 and PT for the Safety Analysis Set. Frequencies and percentages of subjects using each concomitant medication will be presented for the Safety Analysis Set overall, and by treatment group. All medication use will be listed regardless of the timing of the start of the medication.

### **8.8 Pharmacokinetic Analyses**

For all subjects, serum samples will be collected before each dose at time points shown in [Appendix 1](#) to quantify concentrations of KPL-716. Descriptive statistics will be calculated for the serum concentrations of KPL-716 by visit. Individual listings of plasma concentrations will be provided.

Pharmacokinetic data may be used in a subsequent population pharmacokinetic evaluation that will be conducted outside of this study and described in a separate report.

#### **8.9 Biomarker Analyses**

Skin and blood biomarkers levels will be analyzed and summarized in a separate report

#### **8.10 Immunogenicity Analyses**

Serum ADA will be listed and summarized by treatment group and overall using descriptive statistics.

#### **8.11 Gene Expression Analyses**

Biomarker profiles (eg, potentially cytokines, chemokines, and other inflammatory markers) will be analyzed from blood samples. Gene expression will also be analyzed from skin biopsy specimens. Other gene expression analyses may be performed for target genes related to pruritus, inflammation, and/or fibrosis as determined by the Sponsor and summarized in a separate report.

Descriptive statistics and changes from baseline, as applicable, will be calculated for gene expression. No inferential statistical analyses are planned.

#### **8.12            Interim Analyses**

An interim analysis for Phase 2b portion may be conducted after at least 50% subjects complete Week 16 Visit. If the interim analysis is conducted in the Phase 2b part, a two-sided alpha of 0.0001 will be spent. The two-sided alpha level for the final Phase 2b efficacy analysis will be 0.05. Additional details regarding the interim analysis, if performed, will be provided in the SAP along with other analysis plans.

**9                   QUALITY CONTROL AND QUALITY ASSURANCE****9.1               Auditing**

The study may be audited or reviewed by Kiniksa Quality Assurance department, IRB/IEC, and/or regulatory authority at any time. The study site is required to allow for study-related monitoring, audits, IRB review, and regulatory inspections by providing direct access to the study source data and documents.

Measures will be undertaken to protect the confidentiality of records that could identify subjects, ensuring the privacy and confidentiality rules are followed in accordance with applicable regulatory requirements.

**9.2               Monitoring**

The Sponsor will designate a Study Monitor who will be responsible for monitoring this clinical trial. The Study Monitor will monitor the study conduct, eCRF and source documentation completion and retention, and accurate study drug accountability. To this end, the Study Monitor will visit the study site at scheduled intervals per the Sponsor requirements and will be expected to be in frequent contact with the study site through verbal and written communication. It is essential that the Study Monitor has access to all documents, related to the study and the individual subjects, at any time these are requested. In turn, the Study Monitor will adhere to all requirements for subject confidentiality as outlined in the ICF. The Investigator and Investigator's staff will be expected to cooperate with the Study Monitor, to be available during a portion of the monitoring visit to answer questions, and to provide any missing information.

Monitoring to review study drug receipt, inventory, storage, documentation, and handling will be conducted by the study monitor. In Part 2b this activity may be performed by separate unblinded study monitor.

Specific details will be outlined in the Clinical Monitoring Plan.

**10 DATA HANDLING AND RECORD KEEPING****10.1 Data Handling**

The Sponsor's CRO will be responsible for data management of this study, including quality of the data. The study site will be responsible for data entry into the electronic data capture system (EDC) system. A comprehensive validation check program will verify the data. Discrepancies will be generated automatically in the system at the point of entry or added manually for resolution by the study site staff.

The Data Management Plan will outline the quality checks to be performed on the data. Study data transfers will be outlined in Data Transfer Agreements.

**10.2 Case Report Form**

Data will be captured in source documentation at study sites and then entered into the eCRFs or EDC by staff at the study site. Following data entry, the eCRF pages and the data entry will undergo quality control checks in accordance with written procedures. Any discrepancies will be resolved in the database.

Following all data validation steps, the Investigator will sign the completed electronic data prior to any planned interim data analysis snapshots and/or a final database lock.

**10.3 Records**

Records and documents, including signed ICF, pertaining to the conduct of this study must be retained by the study site in accordance with 21 Code of Federal Regulations 312.62(c). No records may be destroyed during the retention period without the written approval of the Sponsor. No records should be transferred to another location or a third-party vendor without a written notification to the Sponsor.

Study records will be maintained by the Sponsor or Designee. Record and document keeping will be detailed in a separate plan.

## 11           **ETHICAL AND REGULATORY CONSIDERATIONS**

### 11.1           **Ethics Committee or Institutional Review Board**

Prior to the start of the study, the following documents will be reviewed and approved by the participating IRB/IEC according to local procedures:

- protocol
- ICF
- subject recruitment procedures (e.g., advertisements)
- any other written information to be provided to subjects.

The IRB will be informed by the Investigator of any changes to the approved protocol.

Any amendments to the protocol will require IRB/IEC approval. Any administrative amendments to the protocol will be provided to IRBs/IECs according to IRB/IEC procedures.

The IRB/IEC will be informed by the Investigator of serious and unexpected SAEs in accordance with the IRB/IEC reporting requirements. The Investigator will provide the IRB/IEC with progress reports per IEB/IEC procedures.

### 11.2           **Regulatory Considerations**

The study will be conducted in accordance with the protocol and with:

- consensus ethical principles derived from international ethics guidelines, including the Declaration of Helsinki and Council for International Organizations of Medical Sciences Ethical Guidelines
- International Conference on Harmonization (ICH) E6 Guideline for Good Clinical Practice
- applicable local laws and regulations.

The Investigator will be responsible for the overall conduct at the study site and adherence to the requirements of the ICH guidelines and all other applicable local regulations.

### 11.3           **Informed Consent**

Prior to starting participation in the study, each subject will be provided with a study-specific ICF that includes all required elements of informed consent per ICH and local regulations. The ICF will give details of the study drug, procedures, and potential risks of the study. Subjects will be instructed that they are free to obtain further information from the Investigator and that their participation is voluntary, and they have the right to voluntarily withdraw from the study at any time.

Following discussion of the study with the study site personnel, subjects will sign and date the ICF in the presence of a qualified staff member to indicate that they are voluntarily giving their informed consent. One copy will be given to the subject, and the original signed ICF will be maintained in the subject's records at the study site.

Skin biopsies are optional in this study.

#### **11.4            Subject Confidentiality**

All personal data collected and processed for the purposes of this study should be managed by the Investigator and his/her staff with adequate precautions to ensure confidentiality and security according to national and/or local laws and regulations on personal data protection.

Sponsor and study vendor databases will similarly be managed and maintained according to national and/or local laws and regulations to prevent unauthorized access, disclosure, dissemination, alteration or loss of information and personal data. In the event of any such data security breach, immediate action will be taken by sponsor and/or study vendor to remedy the breach, assess the extent of data exposure, and implement appropriate measures to limit possible adverse effects.

Monitors, auditors, and other authorized agents of the Sponsor and/or its designee, the ethics committees approving this research, as well as that of any other applicable agency(ies), will be granted secured direct access to the study subjects' original medical records for verification of clinical study procedures and/or data, without violating the confidentiality of the subjects to the extent permitted by the law and regulations. In any presentations of the results of this study or in publications, the subjects' identity will remain confidential.

